### 4.3.3 Exploratory endpoints

| Endpoint title                                                      | Time frame                                         | Unit  |
|---------------------------------------------------------------------|----------------------------------------------------|-------|
| Patient reported outcomes                                    |                                                    |       |
| Patient preference assessed by questionnaire                        | Week 24                                            | %     |
| Change in patient's treatment burden using the Hemo-TEM total score | From baseline (week 0 a ) until week 24 | Score |

| Endpoint title                                                         | Time frame                                                                                         | Unit     |
|-------------------------------------------------------------------------------|-----------------------------------------------------------------------------------------------------------|-----------------|
| Change in PROMIS Short Form v2.0 -Upper Extremity 7a                          | From baseline (week 0 a ) until week 24                                                        | Score           |
| Change in PROMIS Numeric Rating Scale v.1.0 – Pain Intensity 1a               | From baseline (week 0 a ) until week 24                                                        | Score           |
| Change in Haem-A-QoL total score                                              | From baseline (week 0 a ) until week 24                                                        | Score           |
| Change in Haem-A-QoL physical health domain score                             | From baseline (week 0 a ) until week 24                                                        | Score           |
| Physical activity measured by accelerometer                            |                                                                                                           |                 |
| Change in time spend in moderate to vigorous physical activity (MVPA) per day | From baseline to end of the main part (week 24 for the on-demand arm and week 32 for the concizumab arms) | Minutes per day |

aDefined as time of randomisation to on-demand administration or time of start of the new concizumab dosing regimen.

## 5 Trial design

### 5.1 Overall design

This is a prospective, multicentre, open label clinical trial with four arms. The trial aims to evaluate the effect and safety of daily concizumab prophylaxis administered s.c. in patients with HAWI and HBWI. Initially, patients were randomised to concizumab PPX or no PPX or assigned into the non-randomised treatment arms, based on their treatment regimen before entering the trial. After the restart of the trial, the patients will enter the treatment arm they were initially assigned to. New patients eligible for arms 1 and 2 will be randomised to concizumab PPX or no PPX. The main part of the trial is completed for a patient when the patient has completed at least 24 weeks of participation (screening period not included) for patients in arm 1 or 32 weeks of participation (screening period not included) for patients in arms 2,3 and 4. After the main part of the trial, all patients will be offered to continue in the extension part of the trial and receive treatment with concizumab for up to an additional 128 weeks (arms 2–4) or 136 weeks (arm 1); [Figure 1](#).

A *primary analysis cut-off* is defined as when all patients in arm 1 have completed visit 9/9a (or withdrawn) and all patients in arm 2 have completed visit 10a (or withdrawn). Furthermore, a 56-week cut-off is defined as when all patients in arms 2, 3 and 4 have completed visit 13a (or permanently discontinued treatment). At this 56-week cut-off, an additional evaluation will be made assessing bleed related endpoints and safety.

[figure not shown]
After the last patient has been randomised, any patient that due to the COVID-19 pandemic is prevented from restarting the new dosing regimen will no longer be used to determine the primary analysis cut-off and the 56-week cut-off.

After up to 128/136 weeks in extension part the patient will enter the safety follow-up part of the trial. The patient will receive his last dose at home on the day prior to visit 26a. The follow-up part of the trial lasts for 7 weeks and the patient will continue to report bleeding episodes until visit 27a.

In this version of the protocol, patients not already enrolled at the time of the re-start, will be defined as new patients recruited from the non-interventional study NN7415-4322 (explorer 6) and from outside the concizumab programme. New patients can belong to the following categories:

- patients who were in screening phase at the time of the pause
- patients entering from NN7415-4322 (explorer 6)
- new patients coming from outside the concizumab programme.

All of the above-mentioned new patients will start the trial at visit 1a (screening visit).

**Note:** aThe individual maintenance dose will be either 0.15, 0.20 or 0.25 mg/kg concizumab (see Section [9.2.2](#)).

**Abbreviations:** OnD = on demand; PPX = prophylaxis; V = visit

## Figure 1 Trial design

The randomisation between the treatment arms 1 and 2 is stratified according to haemophilia type and bleeding frequency during the 24 weeks prior to screening; see Section [7.2](#). Upon restart, patients will enter the treatment arm they were originally randomised or assigned to. New patients, including patients who were in screening at the time of the pause, will be randomised or allocated to treatment, as outlined below.

### Treatment arms 1 and 2:

Approximately 51 patients (27 HAwI and 24 HBwI), previously treated on-demand, will be randomised 1:2 to no prophylaxis versus concizumab prophylaxis. Patients will be stratified by the haemophilia type and the bleeding frequency.

**Patients randomised to arm 1 before the pause** were instructed to continue their on demand treatment and report data until trial restart. It is expected that all of these patients will have completed at least 24 weeks of on demand treatment when restarting the trials. Upon completion of the main part, the arm 1 patients will start the new concizumab dosing regimen (see Section [5.2.1](#)) and receive up to 136 weeks of concizumab PPX in the extension part of the trial.

**Patients randomised to arm 2 before the pause** have discontinued their concizumab treatment and received available standard of care during the pause. Upon restart, patients who do not fulfil any discontinuation criteria (see Section [8](#)) will receive the new concizumab dosing regimen from visit 2a (described in Section [5.2.1](#)).

**New patients eligible for arms 1 and 2** will be recruited to fulfill the protocol target numbers. New patients eligible for arms 1 and 2 will be randomised as outlined in Section [7.2](#).

### Treatment arm 3:

The HAwI and HBwI patients enrolled into the concizumab phase 2 trial (NN7415-4310 (explorer 4)) at time of transfer will be offered enrolment into arm 3 (approximately 25 patients). It

is required that these patients are on concizumab prophylaxis up until enrolment into the trial. These patients will continue concizumab PPX and have a combined visit 1 and 2. All patients from 4310 were transferred to trial 4311 before the pause. Upon restart, patients will receive the new concizumab dosing regimen.

#### Treatment arm 4:

Arm 4 will include approximately 60 patients previously on prophylaxis with by-passing agents as well as any on-demand patients who are screened at a timepoint where the required number of patients in arms 1 and 2 have been randomised. These patients will, if eligible, be enrolled into the trial and will initiate concizumab prophylaxis at visit 2a. Patients restarting in arm 4 as well as new patients allocated to arm 4 will receive the new concizumab dosing regimen.

#### Patients who were enrolled before the pause

Patients who were randomised or allocated to treatment in this trial before the pause, should re-enter the trial as outlined in [Table 1](#)

**Table 1** Visit overview for patients restarting this trial

| Allocation before the pause | Allocation at restart |
|-----------------------------|-----------------------|
| Arm 1                       | Arm 1 - visit 9a      |
| Arm 2                       | Arm 2 - visit 2a      |
| Arm 3                       | Arm 3 - visit 2a      |
| Arm 4                       | Arm 4 - visit 2a      |

Note: Visit 9a is the first visit in the extension part for arm 1. At visit 9a, the patients in arm 1 will start concizumab PPX.

[Table 2](#) below summarises the expected numbers of randomised/enrolled patients in each arm. In total 136 patients are expected to be enrolled; this includes patients enrolled before as well as after the pause. The aim is to have approximately 15 unique HAwI and HBwI adolescent patients defined as patients between  $\geq 12$  to  $< 18$  years at trial start.

**Table 2** Randomisation/enrolment overview

[figure not shown]
|      | Number of patients randomised/enrolled |       |          |                             |
|------|----------------------------------------|-------|----------|-----------------------------|
|      | Arm 1                                  | Arm 2 | Arm 3    | Arm 4
(PPX or on-demand) |
| HAwI | 9                                      | 18    | Up to 15 | 60                          |
| HBwI | 8                                      | 16    | Up to 10 |                             |

## 5.2 Treatment of patients

### 5.2.1 Concizumab prophylaxis

When patients are randomised/allocated to concizumab prophylaxis they will receive a loading dose of 1.0 mg/kg concizumab at visit 2a (arm 2, 3 and 4) or visit 9a (arm 1) followed by an initial daily dose of 0.20 mg/kg concizumab from treatment day 2. Within an initial 5–8-week dose adjustment period on 0.20 mg/kg concizumab, the patients can be increased or decreased in dose to 0.25 mg/kg or 0.15 mg/kg concizumab. A potential dose adjustment will take place at visit 4a.1 or 9a.3 and will

be based on the concizumab exposure level measured at the previous visit 4a or 9a.2. Patients who have concizumab exposure levels of 200–4000 ng/mL will stay at 0.20 mg/kg concizumab. The new concizumab dosing regimen is shown schematically in [Figure 2](#) and explained in further detail in Section [9.2.2](#).

**Abbreviation:** LD = loading dose

**Notes:** Concizumab exposure level is measured at V4a/9a.2; Potential dose adjustment will take place at V4a.1/9a.3.

## Figure 2 Concizumab dosing regimen upon re-initiation of trial

Doses, including the loading dose, given at PK/PD visits (i.e. visit 2a and 9a) will be administered at the site; all other injections may be administered at home by the patient or caregiver.

Prior to visit 2a, patients must be in a non-bleeding state 48 hour prior to the visit however patients are allowed to have treatment for up to 24 hours prior to visit 2a, except for treatment with aPCC and ByClot® where the wash-out is 48 hours prior to visit 2a.

For patients coming from a PPX treatment regimen, a wash-out of aPCC and ByClot® for 48 hours is required. For other factor-containing products, a wash-out of 2 half-lives of the given product is required.

A pre-filled, multi-dose pen-injector for the drug administration will be provided by Novo Nordisk, details can be found in Section [7.1.1](#).

Use of factor-containing products not associated to a bleed is not allowed, except for diagnostic procedures, intramuscular injections (e.g. vaccinations) and minor surgery, e.g. dental treatment, endoscopies etc.

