| c) Visit will take place after the concizumab exposure levels are available according to in Section 9.2.2                                                                                                                             |
| d) Only patients enrolled after the treatment pause will sign the Informed Consent at visit 1a                                                                                                                                                        |
| e) Only patients enrolled in the trial before the treatment pause and allocated to arm 2, 3 and 4, will re-consent at Visit 2a                                                                                                                        |
| f) Only patients enrolled in the trial before the treatment pause and randomised to arm 1, will re-consent at visit 9a                                                                                                                                |
| g) Only applicable for arm 1 patients, who are receiving concizumab at Visit 9a                                                                                                                                                                       |
| h) Only applicable for patients in arm 2, 3 and 4, who are receiving concizumab at visit 2a                                                                                                                                                           |
| i) Only applicable for patients enrolled in the trial before treatment pause. Site must ensure patients do not violate discontinuation criteria according to Section 8.1 before reinitiating dosing with concizumab                   |
| j) Patients randomised to arm 2 before the treatment pause will not be re-randomised at visit 2a                                                                                                                                                      |
| k) Weight only, except at visit 1 where height is measured                                                                                                                                                                                            |
| l) For patients having concizumab dosing at visit 2a there will be a 24-hour PK session at visit 2a and 9a. Please see details for PK sampling in Section 2.1 . For on-demand patients (arm 1) only the pre-dose sample will be taken |

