### 5.2.2 On-demand treatment

Patients in arm 1 will continue on-demand treatment with their usual bypassing product until visit 9 (end of main part for arm 1). Patients included prior to the treatment pause will re-start the trial at visit 9a; see Section [5.1](#). Novo Nordisk will not provide or reimburse on-demand treatment for patients in arm 1. In the extension part, patients in arm 1 will receive daily concizumab subcutaneous injections (see Section [5.2.1](#)).

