#### **9.5 Pharmacokinetics**

Concizumab will be quantified using a validated ELISA assay. Recombinant human TFPI will be used to capture concizumab. A colorimetric detection signal is obtained by the enzymatic reaction of horseradish peroxidase labelled anti-human IgG4 specific antibodies with the chromogenic substrate TMB (3,3',5,5'-tetramethylbenzidine). The amount of anti-TFPI present in the calibration, quality control and test samples correlate with the obtained signal strength.

Validation of the assay follows current guidelines for bioanalytical method validation. Bioanalytical data will be reported in a bioanalytical report.

The concizumab ELISA will be used to evaluate exposure and pharmacokinetics of concizumab.

For patients dosed with concizumab from visit 2a (patients in arms 2, 3 and 4), two 24-hour PK/PD-sessions will be conducted at visits 2a and 9a. The concizumab dose will be administered in the abdomen and blood samples will be drawn pre-dosing, 3, 6, 9 and 24 hours after dosing. Care must be taken to ensure the 24-hour sample is drawn before the next daily dose of concizumab is administered. At the day of visit 9a patients should not dose themselves at home; the dose will be administered at site followed by blood sampling. The dose should be taken at site in the abdomen and care must be taken to ensure the 24-hour sample is drawn before the next daily dose of concizumab is given.

For patients who had a 24-hour PK profile measured at visit 2 prior to the treatment pause, a new 24-hour PK profile at visit 2a should not be conducted after restart of the trial. For these patients, only pre-dose and 24-hour post-dose samples should be taken at visit 2a. Care must be taken to ensure the 24-hour sample is drawn before the next daily dose of concizumab is administered.

Following items must be recorded in the eCRF:

- Time of lab samples taken
- Time of concizumab dose
- Injection site location

See Section [2.1](#) for the specific timepoints for the PK analysis.

In addition to the two PK/PD sessions, pre-dose concizumab levels ( $C_{trough}$ ) will be measured throughout the concizumab treatment period. These blood samples must be drawn prior to trial product administration as specified in the flowchart in Section [2](#). If the patient has taken the daily

dose of concizumab before collection of the concizumab ELISA sample, then visit 4a (arm 2, 3, 4) and visit 9a.2 (arm 1) should be rescheduled.

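### The bleed-free and wash-out conditions in protocol section 5.2.1 are tied to visit 2a only, although arm 1 receives its first concizumab dose at visit 9a

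*Protocol*

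**What the plan says.** Section 5.2.1 places the start of concizumab at different visits by arm: patients allocated to it are told that "they will receive a loading dose of 1.0 mg/kg concizumab at visit 2a (arm 2, 3 and 4) or visit 9a (arm 1"). The note to Table 1 in section 5.1 agrees: "At visit 9a, the patients in arm 1 will start concizumab PPX". Section 5.2.2 sends the reader back to 5.2.1 for this step: "In the extension part, patients in arm 1 will receive daily concizumab subcutaneous injections".

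The text under Figure 2, still within section 5.2.1, then gives the conditions:

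- No bleeding for 48 hours: "Prior to visit 2a, patients must be in a non-bleeding state 48 hour prior to the visit".
- Bleed treatment is acceptable up to 24 hours before visit 2a.
- aPCC and ByClot are held to a longer interval: "where the wash-out is 48 hours prior to visit 2a".

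A separate paragraph adds a 48-hour wash-out for aPCC and ByClot and two half-lives for other factor products. It names no visit, but it opens with "For patients coming from a PPX treatment regimen".

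**The concern.** Arm 1 patients treat their bleeds with bypassing agents right up to the visit at which concizumab starts, so a recent bleed or injection at visit 9a is foreseeable. Read literally, the conditions bind a new arm 1 patient at week 0, about 24 weeks before any concizumab, and do not bind him at week 24 when the 1.0 mg/kg loading dose is given. A site following the text exactly may give that dose shortly after aPCC or ByClot. Another site may extend the rule to visit 9a on its own initiative, so practice can differ.

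The background makes this worth settling. The programme was paused for thromboembolic events, and section 3.3 records that all three affected patients had treated a bleed shortly before their symptoms began. There is also a small data consequence. Under SAP section 5.1 and Appendix 2, arm 1's visit 9a values are the baseline for descriptive changes in laboratory parameters, including coagulation parameters, and a recent bleed or bypassing dose could shift them.

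**Working it through.** **Text check.** Rules that apply before first dosing, by visit:

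| Rule | Visit 2a | Visit 9a, arm 1 |
|---|---|---|
| 48 hours without bleeding (5.2.1) | yes | not stated |
| Bleed treatment ends 24 hours before (5.2.1) | yes | not stated |
| 48-hour aPCC/ByClot wash-out (5.2.1) | yes | not stated |
| Wash-out for patients coming from prophylaxis (5.2.1) | yes | arm 1 is on demand |
| COVID-19 postponement (8.1.1) | yes | yes |
| Bleed-management education (Appendix 11) | yes | yes |

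The last two rows show that the protocol names both visits when it means both. No other section of the protocol or SAP gives a bleed-free or bypassing-agent interval before visit 9a. Table 1 has arm 1 patients from before the pause re-entering at visit 9a.

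**How often it would matter.** The plan gives no figure, so this is an illustration.

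Inputs: on-demand ABR 18 and yearly over-dispersion 13, range 11 to 15 (section 10.1); 17 planned arm 1 patients, 9 + 8 (Table 2). A lower ABR of 12 reflects the 52-week criterion in section 6.4, which patients from explorer 6 need not meet. Over-dispersion is taken as the yearly variance-to-mean ratio, so 1 + ABR/k = 13 and the gamma shape is k = ABR/12.

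Chance that at least one treated bleed starts in a window of d days:

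m = ABR × d / 365.25; P = 1 − (1 + m/k)^(−k)

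- ABR 18, k = 1.5, 48 hours: m = 0.0986, P = 9.10%; × 17 = 1.55
- ABR 18, 24 hours: m = 0.0493, P = 4.73%; × 17 = 0.80
- ABR 12, k = 1, 48 hours: P = 6.17%; × 17 = 1.05
- ABR 12, 24 hours: P = 3.18%; × 17 = 0.54
- Over-dispersion 11 (k = 18/10 = 1.8) and 15 (k = 18/14 = 1.286), ABR 18, 48 hours: 9.15% and 9.06%
- No over-dispersion: 1 − exp(−0.0986) = 9.4%

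The result barely depends on the over-dispersion. If patients are independent, the chance that at least one of 17 falls in the 48-hour window is 1 − (1 − 0.0910)^17, about 80%; at ABR 12 it is about 66%.

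A bleed that began earlier and is still active also breaches the first condition. Bleed duration is not in the documents. An assumed mean of 1 or 2 days widens the window to 3 or 4 days: m = 0.1478 or 0.1971, P = 13.15% or 16.91%, giving 2.24 or 2.87 of 17. Untreated bleeds are not counted.

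The share of arm 1 bleeds treated with aPCC or ByClot is not given. At shares of 0, 25, 50 and 100%, 17 × 0.0910 × share = 0, 0.39, 0.77 and 1.55 patients within 48 hours.

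The number of arm 1 patients still to be dosed is also not given. The 48-hour expectation is 0.91 per 10 remaining, or 0.46 per 5.

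**The case against.** **The conditions may serve sampling, not safety.** The protocol states no purpose. A clean week-0 sample is a possible aim, and at the first of the two profile visits arm 1 gives little blood: "For on-demand patients (arm 1) only the pre-dose sample will be taken". Against this, for arms 2 to 4 "two 24-hour PK/PD-sessions will be conducted at visits 2a and 9a", yet the later session carries no such conditions. Restarting patients with an earlier full profile, who give only two samples at visit 2a, get no exemption. That pattern suits first dosing somewhat better, but on-treatment sampling is not a pre-treatment baseline and the two-sample patients still need clean samples. The purpose stays open.

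**Bleed treatment is allowed during concizumab.** Section 5.2.3 tells patients to continue dosing through bleeds and their treatment. So a reader who infers that the protocol exposes arm 1 to a demonstrated thrombotic hazard goes beyond the documents. The three affected patients were already on concizumab, and in two cases the factor treatment was relatively high-dose or prolonged. The allowance is conditional, however: aPCC and ByClot are capped, the first treatment is at the hospital with 24 hours' observation, and Table 3 is headed as guidance during concizumab prophylaxis. It does not settle what should precede a first loading dose.

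**The two-half-lives sentence names no visit.** Read as general, it would give some wash-out at visit 9a. Its place in the paragraph on prophylaxis patients makes that the weaker reading, and it would still supply neither a bleed-free interval nor the 48-hour aPCC/ByClot rule.

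**Other controls exist.** The visit 9a dose is given on site, bleeds are reviewed at every visit, and bleed education precedes dosing. These make it likely that the investigator knows of a recent bleed; they do not say what to do about it. The site guidance listed in Table 23 and the figures were not available and may say more.

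**Conclusion.** The gap in the wording is clear: three stated conditions cover visit 2a, and none covers arm 1's first dose at visit 9a. Its importance is minor. A safety benefit is an inference from the first-dose setting and the thromboembolic history; the documents neither demonstrate it nor give the purpose of the conditions.

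A reader might suppose that the efficacy comparison is compromised. It is not. Arm 1's observation period ends when concizumab starts, so the primary analysis and the power are unaffected, and the only data effect is on a descriptive baseline.

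The size, about 9% per patient or 1.5 of 17 for the 48-hour window, rests on the planning ABR of 18 and counts bleed timing, not harm. It is not a bound. The number who could still benefit is probably smaller: the pause ended in August 2020 and protocol version 7.0 dates from June 2021, so some arm 1 patients had probably been dosed already.

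**What to change.** Leave the visit 2a conditions in place for all patients and add one sentence to section 5.2.1: *For arm 1, the same conditions apply before the first concizumab dose at visit 9a; if they are not met, visit 9a is postponed.* Section 8.1.1 already handles COVID-19 this way.

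It is tempting instead to reword the rule as visit 2a for arms 2 to 4 and visit 9a for arm 1. That would not work. Randomisation takes place at visit 2a, so the arm is not known when the conditions must be met, and arm 1 would lose them at its week-0 baseline.

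For arm 1 patients already dosed, list those whose recorded bleed or injection times (section 9.2.3) fall inside the 24- or 48-hour windows. If the conditions are meant for visit 2a alone, say so and give the reason.

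The cost is one sentence by amendment, a letter to sites, and a listing from data already collected. Visit 9a would slip by a day or two for a few patients, often within its ±3-day window. The slightly longer on-demand period fits the endpoint definition, which sets 24 weeks as a minimum. If every arm 1 patient has been dosed, only the listing remains.
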